APPENDIX A.1: Planned laboratory tests	64
Appendix B. Definitions for Adverse Events Monitoring	65
APPENDIX C: Clinical adverse events to be monitored : Symptoms	66
APPENDIX D: LABORATORY VALUES	67
APPENDIX E. FEVER SEVERITY GRADING	69

LIST OF ABBREVIATIONS

[figure not shown]
AE	Adverse Event
CFR	Code of Federal Regulations
CIOMS	Council for International Organizations of Medical Sciences
CONSORT	Consolidated Standards of Reporting Trials
CRF	Case Report Form
DSMB	Data and Safety Monitoring Board
DSMP	Data Safety Monitoring Plan
EC	Ethics Committee
FWA	Federal-Wide Assurance
GCP	Good Clinical Practice
IATA	International Air Transit Association
ICH	International Conference on Harmonisation
IND	Investigational New Drug Application
INS	Peruvian National Institute of Health (Instituto Nacional de Salud)
IRB	Institutional Review Board
CITI	Collaborative Institutional Training Initiative
LR or Lr	Lactobacillus reuteri
MOP	Manual of Procedures
NIDDK	National Institute of Diabetes and Digestive and Kidney Diseases
NIH	National Institutes of Health
OHRP	Office for Human Research Protections
OHSR	Office of Human Subjects Research
PI	Principal Investigator
PID	Personal Identifying Code
PL	Placebo
QA	Quality Assurance
QC	Quality Control
SAE	Serious Adverse Event
SID	Specimen identification code
SOP	Standard Operating Procedure
WHO	World Health Organization

PROTOCOL SUMMARY

Title:	Safety of Lactobacillus reuteri in healthy children aged 2-24 months
Précis:	Phase I double blinded randomized trial of the safety and tolerability of Lactobacillus reuteri DSM 17938 given for five successive days in healthy children. Sixty children will receive study product at a treatment to placebo ratio of 2:1 and followed for 3 months for safety outcomes.

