3.2.1 Primary Outcome Measures

23
24 There are three major areas of safety and tolerability that will be assessed in this phase I
25 trial. The outcome measurements will be compared between the two treatment groups
(Intervention v placebo) with intent to treat analysis.

26
27
28 **1. Evidence of invasive infection resulting from the administration of *L. reuteri* DSM
29 17938.** Baseline and daily temperature measurements will be made during the study
30 period. Complete hemogram with differential count obtained at baseline, on day 5, and
31 on day 28. Vital signs will be monitored daily during the administration of the treatment
32 (days 1-5). The evaluation of all febrile episodes will be done and include a physician
33 exam and the evaluation of blood smears for malaria and blood cultures for the
34 evaluation of possible bacteremia.

35
36 Specific outcome parameters in this category include:

37
38 a. Mean daily temperature
39 b. Incidence of fever on study days 1-5
40 c. Frequency of temperature readings categorized as fever (adjusted for number of
41 subjects per group)
42 d. Number of episodes of *L. reuteri* bacteremia

43
44 **2. Clinical tolerance.** The inclusion of a placebo group will allow for comparisons of daily
45 symptom measurements to be compared between the treatment and placebo group.
The symptoms will be monitored for at household visits, and will be graded as
adverse events according to defined criteria. Symptoms monitored as AEs include
fever, nausea/upset stomach, vomiting, diarrhea, irritability, rash, pruritis, and
wheezing or bronchospasm. Diagnostic microbiology will be performed on all stool
specimens from subjects who develop diarrhea during the 90 days following initiation
of therapy.

46
47 Specific outcome parameters in this category include:

- 1 a. Frequency and severity of symptoms monitored as AEs (adjusted for number of
2 subjects per group)
- 3 b. Frequency of all AEs (adjusted for number of subjects per group)
- 4 c. Frequency of SAEs (adjusted for number of subjects per group)

5

6

7 **3. Evidence of toxicity resulting from the *L. reuteri* DSM 17938 preparation.**

8 Participants will have baseline, day 5, and day 28 assessment of hematologic status and
9 renal and hepatic function. Assessment of renal function will include blood urea nitrogen
10 (BUN) and creatinine (Cr). Assessment of hepatic toxicity will include transaminases

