4 STUDY DESIGN

The study is a single center Phase 1 double blind placebo controlled trial of *Lactobacillus reuteri* DSM 17938 in children aged 2-24 months. The study population is based in a community with a registered clinical trial center in rural Peru where this protocol can be done in a highly controlled setting. The study is intended to enroll healthy children living in a resource constrained setting where chronic undernutrition and diarrheal disease is common, as this is the population that is most likely to receive benefit from the use of this and or other probiotic products for the treatment of acute infectious diarrhea and environmental enteropathy.

Up to 100 subjects will be enrolled in order to obtain the randomization of 60 subjects, who will receive study product or placebo at a ratio of 2:1. Participants will be enrolled between the ages of 8 weeks and 24 months. There will be no age stratification. Participants will be screened with a baseline history and physical examination and laboratory tests to determine the HIV status of the child, as well baseline laboratory tests to evaluate occult infections, hepatic function, and renal function. Upon randomization subjects will be screened and randomized to a treatment arm. Product will be administered under the direct supervision of study staff daily for 5 days. The primary outcome is the safety and tolerability of the product at this dose and formulation. Safety will be assessed by the monitoring of baseline laboratory tests at 5 and 28 days following the initiation of therapy and by AE monitoring. Tolerability will be evaluated by analyzing 28 day diary cards that are distributed to all randomized subjects on which parents record their child's symptoms (specifically fever, anorexia/oral intake, vomiting, diarrhea, irritability, rash, wheezing, or open fields which allows them to describe any issue their child may experience and grade its severity). Secondary outcomes include: 1) The assessment of the duration of shedding of *Lactobacillus reuteri* (Lr) strain DSM 17938 following administration. This will be determined by and endpoint PCR assay for *L. reuteri* done on stool collected on D3, D5, D12, D15, D18, D24, D28, D36 on all participants.

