6.1.3 Product Storage and Stability

1 The study product is to be stored at 2-8°C in multidose subject specific amber vials.
2
3
4 Once opened, the contents of the vial should be dispensed in 10 days.
5
6 The product is administered in the clinical trial center by a member of the study staff in
7 a designated product administration space. This space is adjacent to the dedicated
8 product storage space in the clinic. The dosing is done once daily for 5 days and
9 programmed based on participant and staff convenience. Details of product
10 prescription and vial treatment confirmation upon each dose administration are
11 described in the Manual of Procedures.

12
13 **6.2 Dosage, Preparation and Administration of Study**
14 **Intervention/Investigational Product**
15

16 The individual treatment vial is prepared and labelled by BioGaia. No reconstitution or
17 dilution is needed. The vial will be inverted gently 5 times to assure homogenization and
18 five drops of the suspension will be administered orally to the study subject by study staff
19 that is blinded as to the treatment status of the individual.

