6.5 Assessment of Subject Compliance with Study Intervention/Investigational Product

All treatments are directly administered by study staff. Missed dosages will be documented. In the case that a subject is not available on a study day a 1 day window will be tolerated for the administration of a single missing dose. The daily dose is restricted to a single dose per day, so in this case, the dosing interval would occur over a 6 day period. Follow-up schedule would not be altered from the programmed plan. No more than a single dose will be given this window- if a second dose were to be missed, it would be documented in a protocol deviation form and analyzed per group treatment assignment. Subsequent doses are done at 24 hour intervals from the last dose, but visit scheduling cannot be altered after the first dose is administered.

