16 treatment group. The normal range for each parameter will be used to create categories
17 of low, normal, or high. Any result higher than the upper limit normal (ULN) will be
18 categorized as high, any result lower than the lower limit of normal (LLN) will be
19 categorized as low, and any result within the LLN and ULN will be categorized as normal.
20 The number and percentage of subjects in each shift category from baseline to final
21 evaluation will be shown for each parameter. Only the hematology and blood chemistry
22 tests with a numeric normal range and at least one follow-up value will be analyzed for
23 shifts from baseline. The number and percentage of subjects with clinically significant
24 values will be presented.

25
26 **B. The secondary outcome measurements** are

27
28 1. To determine the duration of shedding of *L. reuteri* DSM 17938 following controlled
29 administration.

30
31 Since the longitudinal nature of the repeated PCR assays results in correlated outcomes,
32 generalized estimating equations (GEE) will be used to model the binary response
33 whether subjects exhibited a positive PCR result during the various period of study. The
34 duration of shedding of *L. reuteri* will be assessed using Kaplan Meier Product limit
35 estimates.

36
37
38
39
40 **11.2 Sample Size Considerations**

1
2
3 The sample size for this Phase 1 safety trial in healthy children aged 2-24 months is
4 determined by historical precedent for safety in human use.

5
6 Enrollment for the prior Phase 1 studies in adults (Safety of LR in Healthy volunteers
7 #NCT00774163) and children (Safety of LR in healthy children 2 to 5 years of age in Peru
8 #NCT02124122) have been able to recruit and retain >95 subject (Phase 1 child study in
9 progress). We have high and similar rates of retention in our other studies with more
10 complexity and participant burden, even among our birth cohorts.³⁷

11
12 Missing data will not be imputed. Data will be analyzed per treatment group assignment
13 after the administration of a single dose of product for all safety and tolerability analyses.
14 Data regarding the duration of carriage will be restricted to those individuals who complete
15 5 days of therapy.

16
17 The amount of subjects in this study will likely be underpowered to detect differences in
18 most secondary outcomes. This is in part due to the lack of information on key

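### Sections 3.2.1 and 11.2 define the primary safety population differently, and neither groups children by product received: an unlikely problem, and cheap to close

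*Combined protocol and SAP*

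**What the plan says.** Section 3.2.1 (Primary Outcome Measures) introduces all three primary areas (invasive infection, clinical tolerance and toxicity) as a comparison of the two arms: "Intervention v placebo) with intent to treat analysis". It sets no dosing condition.

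Section 11.2 (Sample Size Considerations) gives the operating rule: "Data will be analyzed per treatment group assignment", applied "after the administration of a single dose of product for all safety and tolerability analyses". Section 6.5 repeats the grouping for a child who misses a second dose, who is to be "analyzed per group treatment assignment". Section 11.1, which describes the analyses themselves, names no population.

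On handling of the product, section 5.4.1 makes the study code identical to the number on the vial, section 6.1.2 provides one multidose vial per child, and section 6.5 has staff give every dose. Section 6.1.3 refers to the Manual of Procedures for details of how "prescription and vial treatment confirmation upon each dose administration are" described.

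**The concern.** The same primary tables have two written populations. A child who is randomised and never takes product is in the denominator under 3.2.1 and out of it under 11.2.

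The second gap is the grouping. The primary questions are causal questions about exposure: infection or toxicity resulting from the product. If a child assigned to placebo were given active product, both rules would leave that child, and any event the product caused, in the placebo arm. The closed reports to the DSMB (section 9.6) are also built from treatment assignment, so they would carry the same misclassification.

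For a safety hypothesis the direction matters. Undosed children lower the event rate of the arm they sit in. If the product does cause harm, exposure that crosses between arms tends to bring the two rates together. Both would favour the hypothesis that the product is safe, so analysis by assignment is not the cautious choice here.

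**Working it through.** **Arm sizes.** Section 4 states: "Up to 100 subjects will be enrolled in order to obtain the randomization of 60 subjects". The protocol summary gives the ratio: "Sixty children will receive study product at a treatment to placebo ratio of 2:1". So 60 × 2/3 = 40 active and 60 × 1/3 = 20 placebo. There is no power calculation to reproduce: the number is "determined by historical precedent for safety in human use".

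**The two rules side by side.**

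| Child | 3.2.1 | 11.2 |
|---|---|---|
| Dosed with assigned product | counted, as assigned | counted, as assigned |
| Randomised, never dosed | counted, as assigned | not counted |
| Dosed with the other arm's product | counted, as assigned | counted, as assigned |

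The rules disagree in the second row only. In the third row they agree, and neither follows exposure.

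**Can a randomised child go undosed?** Section 7.3 puts randomisation on Day 1, after the symptom check and next to the first dose, which leaves almost no gap. Section 5.4.1 assigns the code when screening is complete, and Appendix A puts the treatment number in the Day 0 column, a period that section 7.3 lets run for up to 14 days. On that timing, a child who fails the Day 1 check could hold a number and never be dosed.

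**Size of the denominator conflict.** The documents give no count of undosed children. Assume 1 to 3, all in one arm, and 3 events in that arm.
- Active: 3/40 = 7.5% by intent to treat; 3/39 = 7.7% to 3/37 = 8.1% among dosed children.
- Placebo: 3/20 = 15.0% by intent to treat; 3/19 = 15.8% to 3/17 = 17.6% among dosed children.

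**Size of the grouping gap.** The documents give no rate of wrong-vial dosing. Assume one placebo-assigned child is given active product throughout, with 4 events among the 40 assigned to active and 2 among the 20 assigned to placebo.
- As assigned: 4/40 = 10.0% v 2/20 = 10.0%.
- As received, if that child had one of the two placebo events: 5/41 = 12.2% v 1/19 = 5.3%, a difference of 6.9 points.
- As received, if that child had no event: 4/41 = 9.8% v 2/19 = 10.5%, a difference of 0.8 points the other way.

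**A single rare event.** Suppose the only event in the trial occurs in that child. As assigned, active is 0/40, with an exact (Clopper-Pearson) two-sided 95% upper limit of 8.8%, and placebo is 1/20 = 5.0%. As received, active is 1/41 = 2.4%, upper limit 12.9%, and placebo is 0/19.

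**The case against.** The strongest reply is that little is at stake in practice. Section 11.2 can be read as the working version of the principle named in 3.2.1, and it already contains the one-dose condition. Wrong-vial dosing would have to get past a code that matches the vial number, one vial per child, dosing by staff and a check at each dose. Harm would not vanish if it did happen: section 11.1 lists SAEs individually, section 9.2.2 makes any bacteremia with the study strain an SAE, and the halting rule in 9.5 turns on similar SAEs whose relation to product cannot be excluded, not on a comparison of arms. Section 15.5 sends protocol deviations to the DSMB, so a detected wrong-vial dose should be reported. The safety analysis is descriptive, and even the worst case above moves one child (Fisher exact p = 0.65 for 5/41 v 1/19).

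Most of this stands, and it sets the weight of the point. It does not reconcile the two sections or supply a rule for a misdosed child. The Data and Safety Monitoring Plan and the Manual of Procedures are separate documents that were not available, so a definition there cannot be excluded.

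A reader might go further and infer that the plan conceals a 6.9-point excess of harm. The documents do not support that. The figure needs a misdosing and an event in the same child, both assumed, and without the event the difference is under 1 point. A reader might also infer that product received is already on record for every dose. Section 6.1.3 says only that confirmation is described in the Manual of Procedures. It does not say that the vial code is written down.

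**Conclusion.** The point holds as a cheap improvement, not as a flaw that threatens the trial's conclusions. The wording conflict is real, is confined to randomised but undosed children, and probably has a small effect: up to 0.6 points in the active arm (8.1 − 7.5) or 2.6 in the placebo arm (17.6 − 15.0) under the assumptions above. The absence of grouping by product received is also real. It matters only if a child is given the other arm's product, which the plan's safeguards make unlikely. If that happens and the child has an exposure-related event, one child can shift the comparison visibly, because one child is 5.0 points of a 20-child arm and 2.5 points of a 40-child arm. All counts of undosed children, misdosed children and events are assumptions; only the arm sizes come from the documents.

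**What to change.** Define one primary safety set and use it in 3.2.1, 6.5 and 11.2: every child given at least one dose, grouped by the product actually received. State how mixed exposure is classified, since one wrong dose among five is more plausible than five. For example, any dose of active product could place the child in the active group for analysis.

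To make this workable:
- Record the vial code on the case report form at each dose.
- Keep the table of all randomised children by assignment as a labelled sensitivity analysis.
- List every randomised child never dosed and every wrong-vial dose.
- Align the time of treatment assignment in 5.4.1, 7.3 and Appendix A.
- Use the same grouping in the closed DSMB tables.

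The cost is a few sentences, one recorded field and one extra table. If misdosing occurs, the primary safety table departs from the strictly randomised groups, and the sensitivity table shows by how much. If none occurs, the grouping is unchanged. A vial code cannot reveal a filling or labelling error at the manufacturer, so this fix does not cover that case.

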Objectives:	
Primary: To assess the safety and tolerability of Lactobacillus reuteri (Lr) strain DSM 17938 in healthy infants and children. Safety will be assessed through the evaluation of adverse effects in both study arms for 90 days following product administration and by laboratory monitoring of CBC, AST, ALT, T. bilirubin, BUN and creatinine prior to product or placebo administration with follow-up assessment at 5 and 28 days. Tolerability will be assessed based on parental report of subjective symptoms of well-being during product administration and thru D28 of the study.
 
Secondary: To evaluate the duration of shedding of Lactobacillus reuteri (Lr) strain DSM 17938 following administration. This will be determined by and endpoint PCR assay for L. reuteri done on stool collected on D3, D5, D12, D15, D18, D24, D28, D36 on all participants.

Population:	The sample size of sixty is expected to include an equal number of healthy boys and girls 2-24 months of age at the time of enrollment from a rural community in Loreto Peru where chronic undernutrition and diarrheal disease are both highly prevalent.
Phase:	I
Number of Sites:	Single site- Loreto, Peru
Study Duration:	7 months
Subject Participation Duration:	3 months
Description of Agent or Intervention:	
1. Active Product: Description Lactobacillus reuteri 17938 suspended in sunflower oil, medium chain triglyceride oil, silicone dioxide. Total viable count of L. reuteri 17938 1×10^8 CFU/5 drops per day for 5 consecutive days
 
2. Placebo: Composition Sunflower oil, medium chain triglyceride oil and silicon dioxide. Total viable count of L. reuteri is zero CFU/ 5 drops.

Estimated Time to Complete Enrollment:	4 months

Schematic of Study Design:

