6.1.2 Formulation, Packaging, and Labeling

Formulation of test product and placebo are the following:

1. Active Product: Description *Lactobacillus reuteri* 17938 suspended in sunflower oil, medium chain triglyceride oil, silicone dioxide. Total viable count of *L. reuteri* 17938 1 x 10^8 CFU/5 drops. Study products supplied generally contain 2-8 x 10^8 CFU/5 drops from the manufacturer, in order to guarantee a potency of at least 1 x 10^8 CFU/5 drops by the product expiration date.

2. Placebo: Composition Sunflower oil, medium chain triglyceride oil and silicon dioxide. Total viable count of *L. reuteri* is zero CFU/ 5 drops.

The product is packaged in a single multidose amber glass vial per participant at a volume several times that required for the 5 day dose. The individual vials are packed in reinforced boxes for shipping with a temperature logging.

The label contains the following information

Name of Study: Safety of *Lactobacillus reuteri* in healthy children ages 2-24 months in Peru

BioGaia Drops Dose: 5 drops per dose Store at 2-8C Shake well before using

Test article code: xxxxxxxx Discard 10 days after opening Exp date: yyyy Batch No:

zzzz

Responsible MD: [name], Johns Hopkins University

Manufactured for BioGaia AB, Stockholm Sweden

Caution: New Drug- Limited to investigational use

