11.1 Study Hypotheses and Analysis

A. The primary hypotheses are that *L. reuteri* therapy at the specified dose is safe and well-tolerated in children aged 2-24 months. There are three areas of safety and tolerability that will be assessed in this Phase 1 trial.

- 1. Evidence of bacteremia or invasive infection resulting from the administration of *L. reuteri* 17938.** Baseline and daily temperature measurements will be made during the study period during the product administration phase and then on all scheduled home visits. Complete blood counts with differential counts will be obtained at baseline, on day 5, and on day 28. The evaluation of all documented febrile episodes will include an examination by a physician, and thick smear for malaria, and blood culture for the evaluation of bacteremia if the temperature is greater than 39°C using temporal artery probe measures.

Specific outcome parameters in this category include:

- a. Mean daily temperature
- b. Incidence of fever on study days 1-5
- c. Frequency of temperature readings categorized as fever (adjusted for number of subjects per group)
- d. Number of episodes of *L. reuteri* bacteremia

2. Evidence of toxicity resulting from the *L. reuteri* DSM 17938 preparation.
Participants will have baseline, day 5, and day 28 assessment of hematologic status and

1 renal and hepatic function. Assessment of renal function will include blood urea nitrogen
2 (BUN) and creatinine (Cr). Assessment of hepatotoxicity will include transaminases
3 (AST, ALT) and total bilirubin. Hematologic status will be determined by CBC to
4 measure hemoglobin count and absolute neutrophil count, as mentioned above.

5
6 Specific outcome parameters in this category include:

7
8 a. Mean values for laboratory tests monitored (adjusted for number of subjects per
9 group). These are listed in Appendix D.
10 b. Frequency of out of range values for laboratory tests monitored (adjusted for number
11 of subjects per group). These are listed in Appendix D.

12
13 2. **Clinical tolerance.** The inclusion of a placebo group will allow for comparisons of the
14 prevalence of daily symptom measurements between treatment groups. The
15 symptoms monitored on the daily diary card (fever, anorexia/decreased oral intake,
16 vomiting, diarrhea, irritability, rash, itching, wheezing) are graded by the parent(s) of
17 the participant as mild, moderate, severe, or very severe. Parents report of severity

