participants. This training, which will occur prior to the study and reinforced during the
study, will be documented in the study file for review by study monitors.

16

17 Laboratory protocols

18 Laboratory protocols for the collection, registration and barcoding of all biologic samples
19 will be detailed.

20

21 Product Assurance

22 The Certification of Assurance of the study product, obtained by the product supplier, will
23 contain the following information.

24

25 Identity

26 Identity of the test product will be confirmed by standard carbohydrate utilization tests (API
27 50CH test (BioMerieux) pattern and the plasmid profile of the strain will be documented.

28

29 Purity

30 Information on the content of *Salmonella*, *E. coli*, yeast and mold, and total aerobic count
31 per USP <61>.⁴³ Evaluation for contamination with *Shigella* will be by FDA protocol BAM
32 Chapter 6.). The release limit of *Salmonella*, *Shigella* and *E. coli* is absent in 10g of
33 product, yeast and mold < 100 CFU/g and total aerobic count < 1000 CFU/g.

34

35 Viable counts of probiotic product strain

36 Existing laboratory protocols will be employed, with modifications as necessary, for
37 quantification of the viable count of product strain (name protocol). Viable counts will be
38 performed prior to study enrollment and every month following study initiation until the last
39 dose of product is administered. Tolerance for variability will be \pm 1 log CFU count. If the
40 results are not within this range, the product will be re-analyzed from two vials from the
41 same stock. If again not within range, this stock will be discarded and replaced with new
42 study product provided by BioGaia, the product manufacturer.

43

44 All study personnel engaged in study activities must have training documented in the form

1 of signatures on training logs. For laboratory scientists, this includes practicums
2 demonstrating test proficiency in assay performance and the correct storage and naming
3 of experimental files. Upon completion of testing, they sign the SOP to acknowledge
4 proficiency certification and compliance with the protocol SOP.

5

6

7 **Quality Control**

8 CRFs and source documents will be reviewed for completeness by a field or data entry
9 personnel daily and forms will be reviewed on site by the Study Coordinator, the study
10 physician, and /or overseeing investigators. Upon completion, forms are further evaluated

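### The ±1 log viable-count tolerance in section 13 can pass product below the 1 × 10^8 CFU potency in section 6.1.2, the dose for which safety is to be concluded

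*Combined protocol and SAP*

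**What the plan says.** The Protocol Summary gives the active product as 1 × 10^8 "CFU/5 drops per day for 5 consecutive days". The primary hypothesis in section 11.1 is that *L. reuteri* "therapy at the specified dose is safe and well-tolerated in children aged 2-24 months", so the conclusion is tied to that figure.

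Section 6.1.2 describes an overage: "Study products supplied generally contain 2-8 x 10^8 CFU/5 drops". The reason it gives is "in order to guarantee a potency of at least 1 x 10^8 CFU/5 drops by the product expiration date". The named dose is therefore also the potency floor.

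Section 13, under viable counts, sets the site check. "Tolerance for variability will be" ±1 log CFU, and the text does not say what value the tolerance is centred on. Counts are to be "performed prior to study enrollment and every month following study initiation until the last" dose has been given. Product that falls outside the tolerance is counted again from two vials of the "same stock. If again not within range, this stock will be discarded and replaced with new" product from the manufacturer.

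The analyses in section 11.1 and the report contents listed in section 11.3.1 do not include the measured counts. Section 12 makes the viability tests available to auditors.

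**The concern.** Section 2.3.1 offers the team's own viability and identity testing as one of the safeguards for this trial. A reader would expect that testing to show whether the children received the dose named in the hypothesis. A tolerance of one log either way is wide for that purpose, and without a reference value the actual limits are unknown.

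What is at stake is the label on the conclusion. Sixty children at 2:1 gives 40 on active product. If none of the 40 has a given event, the one-sided 95% upper bound on its rate is 1 − 0.05^(1/40) = 7.2%. That bound belongs to the potency actually swallowed. If the product had drifted well below 1 × 10^8 and still passed, the bound would be quoted for a dose that was not given. No endpoint, comparison, sample size or halting rule changes.

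**Working it through.** **Inputs.** Tolerance ±1 log (section 13), taken as base 10, which the text does not state. Reference value R: not stated. Candidates are the named dose, 1 × 10^8, and the two ends of the supplied range, 2 × 10^8 and 8 × 10^8 (section 6.1.2). Potency floor: 1 × 10^8 CFU per 5 drops (section 6.1.2).

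**Accepted range.** Lower limit = R × 10^−1; upper limit = R × 10^+1; width = 10R ÷ 0.1R = 100-fold for any single R.

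| R (CFU/5 drops) | Lower limit | Upper limit | Lower limit as share of 1 × 10^8 |
|---|---|---|---|
| 1 × 10^8 | 1 × 10^7 | 1 × 10^9 | 10% |
| 2 × 10^8 | 2 × 10^7 | 2 × 10^9 | 20% |
| 8 × 10^8 | 8 × 10^7 | 8 × 10^9 | 80% |

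**Which reference would remove the conflict?** The lower limit reaches the floor only if 0.1R ≥ 1 × 10^8, that is R ≥ 1 × 10^9. That is above the top of the stated supply range, so no reference within that range reconciles the two sections.

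**Loss tolerated if R = 1 × 10^8.** Product supplied at 2 × 10^8 could lose 1 − (1 × 10^7 ÷ 2 × 10^8) = 95% of its viable cells (1.30 log) before reaching the lower limit. Product supplied at 8 × 10^8 could lose 1 − (1 × 10^7 ÷ 8 × 10^8) = 98.75% (1.90 log).

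**Allowing for counting error.** The documents give no assay standard deviation, so 0.1, 0.2 and 0.3 log are assumed here. With R = 1 × 10^8 and normal error on the log10 scale, the chance that a single count falls inside the limits is Φ((9 − m)/SD) − Φ((7 − m)/SD), where m is the log10 of the true content.

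| True content | SD 0.1 | SD 0.2 | SD 0.3 |
|---|---|---|---|
| 2 × 10^7 (one fifth of the floor) | 99.9% | 93.4% | 84.2% |
| 8 × 10^8 (top of normal supply) | 83.4% | 68.6% | 62.7% |

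Stock at one fifth of the floor would usually pass on the first count, and the re-test can only raise the chance that it is kept. Product at the top of the normal range is only log10(1 × 10^9 ÷ 8 × 10^8) = 0.10 log below the upper limit. A single count on it would fall outside about 17% to 37% of the time. Under this reference and these assumed errors, the rule is more lenient to weak product than to product supplied as described.

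**The case against.** The best defence is that section 13 states a tolerance for variability, perhaps of the assay, and nowhere says that the site count enforces the manufacturer's floor. Section 6.4 places the viability tests in laboratory SOPs and a product assurance plan. Those are not among the documents and may hold the reference value and a tighter limit. Other controls also make a large shortfall unlikely: the supplied overage, an initial certificate of analysis and temperature-monitored shipment (section 6.4), storage at 2-8°C (section 6.1.3), an 18-month shelf life (section 6.1.1), and only four months of enrolment (section 4). All of this stands as an argument about likelihood. It does not change the fact that section 13 decides whether stock is kept, and that its limits and section 6.1.2 disagree.

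Some stronger readings are tempting, and the documents do not support them:

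- *Stock at one tenth of the minimum passes.* This holds only if the tolerance is centred on 1 × 10^8. On the other references the limit is 20% or 80% of the minimum.
- *The accepted range is 400-fold.* That figure joins the lower limit for 2 × 10^8 to the upper limit for 8 × 10^8 (8 × 10^9 ÷ 2 × 10^7 = 400). It is not a range around any single reference.
- *Product above 1 × 10^8 undermines the safety conclusion to the same degree.* Section 6.1.2 discloses the overage, and section 2.2 describes much higher doses as safe. A clean result above 1 × 10^8 would support 1 × 10^8, provided risk does not fall as dose rises. On the high side the matter is accurate labelling of exposure.
- *Section 2.2 shows safety differing between 10^7, 10^8 and 10^9.* It groups 10^8 to 10^9 as one effective range. The fall-off it reports below 10^8 is in efficacy.

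**Conclusion.** The point holds on the low side. For a reference of 1 × 10^8, 2 × 10^8 or 8 × 10^8, the section 13 tolerance has a lower limit of 1 × 10^7, 2 × 10^7 or 8 × 10^7. Each is below the 1 × 10^8 in section 6.1.2. Followed as written, the plan could keep such stock in use and still report safety at the named dose, and nothing in the available text would show a reader that this had happened.

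A reader might infer that children will be given weak product. The documents do not say so, and the overage and cold chain point the other way. The finding is that the written check would not reliably detect a shortfall.

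The verdict assumes that the tolerance is on the base-10 scale, that its reference is the named dose or lies within the supplied range, and that no tighter limit in the unseen SOPs or product assurance plan overrides section 13. If one does, the protocol should say so, and the point reduces to a missing cross-reference plus the reporting of potency.

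**What to change.** 1. Name the reference value for the ±1 log tolerance in section 13, and reconcile the resulting limits with the potency in section 6.1.2. The limits are for the sponsor and manufacturer to set. If they are already set in the SOPs or product assurance plan, cite them.
2. Add to section 11.1 that the measured CFU per 5 drops, before enrolment and at each monthly count, will be reported with the safety results.
3. Word the safety conclusion for the potency actually delivered over the dosing period.

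The cost is wording in sections 6.1.2, 11.1 and 13 and one short table. The counts are already planned, so no visit, sample or participant is added. The downside is that a reconciled lower limit might lead to a stock being replaced, with some delay; section 13 already provides for replacement.
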